12.4 Technical complaints and technical complaint samples

12.4.1 Reporting of technical complaints

All technical complaints on any of the following products:

- Concizumab B 100 mg/mL, solution for injection in a 3 ml cartridge
- NovoPen® 4
- Novo Nordisk needles
- Turoctocog alfa 2000 IU/vial, powder for solution for injection in a vial
- 0.9 % sodium chloride 4.0 mL prefilled syringe
- Novo Nordisk trial injection kit

Protocol
 Trial ID:NN7415-4255
 UTN:U1111-1179-3872
 EudraCT no.:2016-000614-29

~~CONFIDENTIAL~~

Date:	05 May 2017	Novo Nordisk
Version:	2	
Status:	Final	
Page:	90 of 124	

which occur from the time of first usage of the product until the time of the last usage of the product, must be collected and reported to Customer Complaint Centre, Novo Nordisk.

Contact details (fax, e-mail and address) are provided in [Attachment I](#) to the protocol.

The investigator must assess whether the technical complaint is related to any AEs, AESIs and/or SAEs.

Technical complaints must be reported on a separate technical complaint form:

- One technical complaint form must be completed for each affected DUN
- If DUN is not available, a technical complaint form for each batch, code or lot number must be completed

The investigator must complete the technical complaint form in the eCRF within the following timelines of the trial site obtaining knowledge of the technical complaint:

- Technical complaint assessed as related to an SAE **within 24 hours**
- All other technical complaints **within 5 calendar days**

If the eCRF is unavailable or when reporting a technical complaint that is not patient related, the information must be provided on a paper form by fax, e-mail or courier to Customer Complaint Center, Novo Nordisk, within the same timelines as stated above. When the eCRF becomes available again, the investigator must enter the information on the technical complaint form in the eCRF.

12.4.2 Collection, storage and shipment of technical complaint samples

The investigator must collect the technical complaint sample and notify the monitor **within 5 calendar days** of obtaining the sample at trial site. The monitor must coordinate the shipment to Customer Complaint Centre, Novo Nordisk (the address is provided in [Attachment I](#)) and ensure that the sample is sent as soon as possible. A copy of the technical complaint form must be included in the shipment of the sample. If several samples are returned in one shipment, the individual sample and the corresponding technical complaint form must be clearly separated.

The investigator must ensure that the technical complaint sample contains the batch, code or lot number and, if available, the DUN. All parts of the DUN should be returned.

If the technical complaint sample is unobtainable, the investigator must specify on the technical complaint form why it is unobtainable.

Storage of the technical complaint sample must be done in accordance with the conditions prescribed for the product.

Protocol
 Trial ID:NN7415-4255
 UTN:U1111-1179-3872
 EudraCT no.:2016-000614-29

~~CONFIDENTIAL~~

Date:	05 May 2017	Novo Nordisk
Version:	2	
Status:	Final	
Page:	91 of 124	

12.5 Pregnancies

12.5.1 Pregnancies in female partners of male patients

Male patients must be instructed to notify the investigator if their female partner becomes pregnant during the trial, except in the screening period (from visit 1 to dosing at visit 2). At the last scheduled visit, male patients must be asked if their female partner has become pregnant.

If a female partner has become pregnant during the trial, the investigator must follow-up on the pregnancy outcome and until the newborn infant is one month of age, irrespective of whether the trial is completed or not. The investigator must ask the male patient and assess, if the pregnancy outcome is normal or abnormal.

When the pregnancy outcome is **normal** this information is recorded in the patient's medical record only, no further information is collected and reported to Novo Nordisk. When the pregnancy outcome is **abnormal** (i.e. congenital anomalies, foetal death including spontaneous abortion and/or any anomalies of the foetus observed at gross examination or during autopsy), the following must be reported by the investigator to Novo Nordisk electronically (e.g. in PDF format) or by fax:

1. Reporting of pregnancy information

Information from the male patient has to be reported on the Paternal Form. Furthermore, information from the female partner (including information about the pregnancy outcome and health status of the infant until the age of one month) has to be reported on the Maternal Forms 1A, 1B and 2, after an informed consent has been obtained from the female partner.

Initial reporting and follow-up information must be reported within **14 calendar days** of the investigator's first knowledge of initial or follow-up information.

2. Reporting of AE information

The following AEs in the foetus and newborn infant have to be reported:

- Non-serious AEs evaluated as possible/probably related to the father's treatment with the trial product(s).
- SAEs in the foetus and newborn infant - whether or not related to the father's treatment with the trial product(s). This includes an abnormal outcome - such as foetal death (including spontaneous abortion) and congenital anomalies (including those observed at gross examination or during autopsy of the foetus).

Forms and timelines for reporting AEs:

Non-serious AEs:

- Paper AE form^a **within 14 calendar days** of the investigator's first knowledge of the initial or follow-up information to the non-serious AE.

SAEs:

Protocol
 Trial ID:NN7415-4255
 UTN:U1111-1179-3872
 EudraCT no.:2016-000614-29

~~CONFIDENTIAL~~

Date:	05 May 2017	Novo Nordisk
Version:	2	
Status:	Final	
Page:	92 of 124	

- Paper AE form^a **within 24 hours** of the investigator's first knowledge of the SAE.
- Paper safety information form **within 5 calendar days** of the investigator's first knowledge of the SAE.
- **SAE follow-up information** to the AE form and/or safety information form **within 24 hours** of the investigator's first knowledge of the follow-up information.

^a It must be clearly stated in the AE diagnosis field on the AE form if the event occurred in the patient, foetus or new born infant.

Any queries or follow-up requests from Novo Nordisk to non-serious AEs, SAEs and pregnancy forms must be responded to by the investigator **within 14 calendar days** from the date of receipt of the request, unless otherwise specified in the follow-up request.

12.6 Precautions and/or overdose

Dose limiting toxicities of concizumab has not been investigated in clinical trials.

There have been no reports about overdosing of concizumab and therefore no experience with overdose and overdose reactions exists. In case of a concizumab overdose, symptomatic medical treatment according to the clinical condition should be applied. No antidote exists in case of concizumab overdose.

Any overdose should be reported as an AE, with or without clinical manifestations. Overdoses are considered medication errors.

Treatment should be as appropriate and in accordance with hospital practice and guidelines.

12.7 Rules for putting enrolment on hold

If one of below mentioned criteria is fulfilled, enrolment of additional patients in the clinical trial program will be placed on hold. An urgent safety committee meeting will be scheduled to decide further actions. Dosing of patients on treatment may continue while further evaluation is made by the safety committee. A substantial amendment with relevant data must be submitted to the regulatory authorities to support restart of the trial.

- Significant thromboembolic event*
- Event of DIC
- Anaphylactic reaction related to trial drug administration
- Death of trial patient which may be related to the trial product
- Two or more other trial product related SAEs similar in nature have been reported and/or detected by laboratory measurements
- Trends in AEs, clinical observations or laboratory parameters which raise concerns about the safety of continued treatment

Protocol
 Trial ID:NN7415-4255
 UTN:U1111-1179-3872
 EudraCT no.:2016-000614-29

~~CONFIDENTIAL~~

Date:	05 May 2017	Novo Nordisk
Version:	2	
Status:	Final	
Page:	93 of 124	

* Superficial thrombophlebitis or venous thrombosis associated with indwelling catheters is not considered a significant thromboembolic event unless evaluated as such by the investigator

If two or more other trial product related SAEs similar in nature have been reported and/or detected by laboratory measurements, or if trends in AEs, clinical observations or laboratory parameters raise concerns about the safety of continued treatment, the safety committee (see section [12.8.1](#)) will then decide whether further dosing of any patients in the clinical trial program should be continued, paused or discontinued.

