5.2 Rationale for trial design

ExplorerTM5 is a phase 2, clinical proof of concept (CPoC) and safety trial. The trial aims to substantiate CPoC that concizumab has the potential to prevent bleeding episodes in haemophilia patients without inhibitors. A dose escalation design will allow cautious dose escalation in order to choose the efficacious and safe concizumab dose for the individual patient from the selected dose regimen Concizumab 0.15 mg/kg (with two potential dose-escalation steps, 0.20 mg/kg and 0.25 mg/kg) given s.c. once daily will be investigated.

The duration of 24 weeks for the main part of the trial is deemed necessary in order to obtain information on the annual bleeding rate (ABR) during concizumab prophylaxis. The duration of the extension part of the trial will be 52 weeks and will provide further information on long-term efficacy, i.e. ABR, and also provide additional safety data upon 76 weeks treatment with concizumab.

A total of 33 patients are planned to receive concizumab s.c. once daily in this single arm trial, please see [Figure 5-1](#).

The concizumab dose regimens will be starting with 0.15 mg/kg with the possibility to escalate to 0.20 mg/kg and 0.25 mg/kg, see section [5.3.1](#).

Daily dosing with 0.15 mg/kg aims to ensure steady-state levels of concizumab plasma concentrations above 100 ng/mL for the majority of the patients starting on this dose. The PK

Protocol
 Trial ID:NN7415-4255
 UTN:U1111-1179-3872
 EudraCT no.:2016-000614-29

~~CONFIDENTIAL~~

Date:	05 May 2017	Novo Nordisk
Version:	2	
Status:	Final	
Page:	31 of 124	

results from explorer^{TM3} showed exposure-response in terms of fewer bleeding episodes recorded for patients who reached plasma concentrations of concizumab above 100 ng/mL see [Figure 3–1](#). The minority of patients which are predicted to have steady-state plasma concentrations below this threshold are expected to experience bleeding episodes and therefore will have the opportunity to be dose-escalated to the dose of 0.2 mg/kg. A further dose escalation to 0.25 mg/kg per day is permitted, again based on the bleeding rate, see section [5.3.1](#).

Figure 5–2 Individual predicted concizumab concentration profiles for all concizumab-treated patients in explorer^{TM2} (n=4 patients) and explorer^{TM3} (n=18 patients). The horizontal lines indicate 100 ng/mL, and the shaded areas represent the full range (min-max) of the individual predicted profiles¹.

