5.3 Treatment of patients

Table 5–1 List of products provided by Novo Nordisk

Compound Name	Strength	Dosage form	Route of administration	Treatment period
Concizumab B²,	100 mg/mL	3 mL solution in a 3 mL cartridge ³ .	S.c. administration using NovoPen [®] 4	For prophylactic treatment for 76 weeks.
Turoctocog alfa (NovoEight[®])⁴, Sodium chloride solution 4ml	2000 IU/vial	Powder for solution for injection Solvent for solution for i.v. injection used for reconstitution of turoctocog alfa.	I.v. administration	For treatment of breakthrough bleeding episodes (or prophylaxis in the screening and follow-up phases), at the discretion of the treating physician (patients may choose to use other familiar pre-trial FVIII drug). For further information see section 5.3.2

Concizumab will be given s.c., once daily for a total dosing period of 76 weeks.

The NovoPen[®]4 injector will be supplied by Novo Nordisk and used for the s.c. administration of concizumab. It will be labelled in accordance with national legislation and a copy of the label can be found within the Trial Materials Manual, see Section [9.1](#).

The first dose of concizumab will be given at the trial site under medical supervision. After the initial dose the patient must be observed for potential emergence of AEs/safety signals for at least 2 hours at the trial site. At the screening visit and the first scheduled treatment visit patients will be trained in s.c. administration of concizumab with NovoPen[®] 4 and in the use of eDiary.

Investigational medicinal product (IMP)

³ Not to be confused with the daily injected volume (~150 µL, depending on dose strength and body weight)

⁴ Non-investigational medicinal product (NIMP)

Protocol
Trial ID:NN7415-4255
UTN:U1111-1179-3872
EudraCT no.:2016-000614-29

~~CONFIDENTIAL~~

Date:	05 May 2017	Novo Nordisk
Version:	2	
Status:	Final	
Page:	34 of 124	

In case safety concerns meet the criteria (See section [12](#)) for putting enrolment of additional patients on hold, further enrolment in the trial will be halted. Dosing of patients on treatment may continue while further evaluation is made by the safety committee. In case of other safety concerns all available data will be evaluated by the DMC see Section [12.8.2](#).

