5.3.1 Dose escalation

Bleeding episodes will be assessed during the trial both at scheduled visits and also between visits. The first 2 weeks of the treatment with concizumab 0.15 mg/kg is considered as a run-in period. Hence the bleeding episodes occurring during the first 2 weeks should not influence a dose escalation decision.

All spontaneous bleeding episodes (sBEs) are counted from 2 weeks after visit 2 (first-dose visit) until visit 16 (end-of-treatment visit), i.e. a total of 74 weeks. Dose-escalation will be based on the number of spontaneous, treated bleeding episodes in patients within preceding 12 weeks. However, before dose-escalation can occur, to ensure the safety of the patients, the investigator must take into account the full clinical picture the patient is presenting with and all available laboratory results, including coagulation parameters.

Dose 0.15 mg/kg:

When a sBE occurs, the investigator will determine if ≥ 3 sBEs have occurred within the preceding 12 weeks since visit 2+2weeks (including the current sBE). If yes, and if investigator deems it safe, the patient will have to be dose escalated from 0.15 to 0.20 mg/kg at the next scheduled visit. If the investigator judges that this visit is scheduled too late, he/she should contact the patient for an unscheduled visit.

Dose 0.20 mg/kg:

When an sBE occurs, the investigator will determine if ≥ 3 sBEs have occurred within the preceding 12 weeks (including the current sBE), counting only new sBEs from the beginning of the 0.20 mg/kg treatment period. If yes, and if investigator deems it safe, the patient will have to be dose escalated from 0.20 to 0.25 mg/kg at the next scheduled visit. If the investigator judges that this visit is scheduled too late, he/she should contact the patient for an unscheduled visit.

Dose 0.25 mg/kg:

Patients are not dose escalated further regardless of the number of sBEs. When an sBE occurs, the investigator will determine if ≥ 3 sBEs have occurred within the preceding 12 weeks (including the current sBE), counting only the new sBEs from the beginning of the 0,25mg/kg treatment period. If yes, then the patient must be discontinued from treatment due to lack of efficacy, see Section [6.4](#).

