8.1.9.4 Visits 4, 5, 6, 7 and 8 (Assessment visits)

Visits 4, 5, 6, 7 and 8 are to be scheduled on trial day 29 (4 weeks), day 57 (8 weeks), day 85 (12 weeks), day 113 (16 weeks) and day 141 (20 weeks) respectively with a visit window of \pm 7days.

Patients should treat themselves at home according to the dosing schedule regardless of when visits 4, 5, 6, 7 and 8 are scheduled

Patients will be asked to complete the PRO questionnaires before any other trial related activities are performed according to section [8.6](#);

- PGI-C
- Hemo-TEM

Assessments are to be performed according to [Table 2-1](#) and the assessment results from concomitant medication, vital signs, Body measurements (weight only) and details of adverse events must be entered into the eCRF.

Investigator is to perform compliance check of treatment and reporting of bleeding episodes through reviewing collected data from the eDiary. Based on the assessment of any spontaneous bleeding episodes the investigator must evaluate if an escalation of the concizumab doses is needed according the escalation rules described in section [5.3.1](#). All decisions to escalate the concizumab dose must be recorded in the eCRF.

In order to determine the correct amount of the patient's daily dose of concizumab, until next scheduled visit, investigator will consult the dosing-table in the TMM on basis of the patient's current body weight. Investigator will communicate any corrections in the daily dose of concizumab to the patient and record the dose for the coming home treatment period in the eCRF.

A dispensing call must be performed in the IWRS.

At the visit the patient will be provided with trial product (concizumab and if necessary rFVIII (turoctocog alfa)) and injection kits to be able to conduct home treatment until next scheduled visit. The patient will be asked to return all used, partly used and unused concizumab cartridges and turoctocog alfa (FVIII) during the trial as instructed by the investigator. Drug accountability must be performed at all visits for concizumab and rFVIII (turoctocog alfa) including injection kits, if applicable.

At visit 8 patients should be reminded that treatment with concizumab must take place after the blood sampling at visit 9.

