If the eCRF is unavailable, the concerned AE information must be reported on a paper AE form and sent to Novo Nordisk by fax, e-mail or courier within the same timelines as stated above. When the eCRF becomes available again, the investigator must enter the information on the form into the eCRF.

Contact details (fax, telephone, e-mail and address) are provided in the investigator trial master file.

Timelines are for the completion of forms from the time of investigator's awareness
 AEs requiring specific event forms are described in Section 12.1.5 and 12.1.6

AE: Adverse event **AESI:** Adverse event of special interest **SIF:** Safety information form

Protocol
 Trial ID:NN7415-4255
 UTN:U1111-1179-3872
 EudraCT no.:2016-000614-29

~~CONFIDENTIAL~~

Date: 05 May 2017
 Version: 2
 Status: Final
 Page: 88 of 124

Novo Nordisk

Figure 12–1 Reporting of AEs

Novo Nordisk assessment of AE expectedness:

Novo Nordisk assessment of expectedness is performed according to the following reference documents: Investigator’s Brochure; Current version and any updates thereto.

Reporting of trial product-related SUSARs by Novo Nordisk:

Novo Nordisk will notify the investigator of trial product-related suspected unexpected serious adverse reactions (SUSARs) in accordance with local requirements and ICH GCP¹. In addition, the investigator will be informed of any trial-related SAEs that may warrant a change in any trial procedure.

In accordance with regulatory requirements, Novo Nordisk will inform the regulatory authorities, including EMA, of trial product-related SUSARs. In addition, Novo Nordisk will inform the International Review Boards/Independent Ethics Committees (IRBs/IECs) of trial product-related SUSARs in accordance with local requirement and ICH GCP¹, unless locally this is an obligation of the investigator.

Novo Nordisk products used as concomitant medication or non-investigational medicinal product:

If an AE is considered to have a causal relationship with a Novo Nordisk marketed product used as non-investigational medicinal product rFVIII (turoctocog alfa) *or* concomitant medication in the trial, it is important that the suspected relationship is reported to Novo Nordisk, e.g. in the alternative aetiology section on the safety information form. Novo Nordisk may need to report this adverse event to relevant regulatory authorities.

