17.1 Sample size calculation

The sample size calculation has been determined taking the small patient population into account, while also aiming for an acceptably narrow 95% confidence interval for the ABR.

Sufficient inference on bleeding episodes for the primary CPoC criterion is judged to be accommodated by 30 patients.

It is expected that the treatment duration of the main part allowing for escalation time for some patients is on average 6 months in the below calculations.

When evaluating the power of the negative binomial analysis referred above, an annual bleeding rate of 4 is assumed for the end dose concizumab regimen, respectively in combination with an over-dispersion of 6. The power for concluding a bleeding rate lower than 12 then becomes approximately 95%. The power under varying values of true ABR and over-dispersion for the primary CPoC criterion are shown below in [Table 17-1](#).

Table 17-1 Power in comparison between concizumab prophylaxis treatment and an ABR threshold of 12 under different assumptions of ABR and over-dispersion.

Power	Over-dispersion		
	5	6	7
4	99%	95%	92%
5	95%	90%	86%
6	87%	81%	72%

Protocol
 Trial ID:NN7415-4255
 UTN:U1111-1179-3872
 EudraCT no.:2016-000614-29

~~CONFIDENTIAL~~

Date:	05 May 2017	Novo Nordisk
Version:	2	
Status:	Final	
Page:	101 of 124	

For the secondary CPoC criterion that includes data prior to potential dose escalation, it is expected that the treatment duration of the main part is on average 8 months with an average ABR of 5.4 for the concizumab treated patients. This yields a marginal power of approximately 87% for the secondary CPoC criterion.

In prior Novo Nordisk trials conducted in haemophilia patients, the typical 1-year over-dispersion for non-inhibitor patients on prophylaxis with FVIII or FIX has been in the range 4-8, implying 24 weeks over-dispersion of 3-5 (e.g. in NN7008-3543, NN7088-3859 and NN7999-3747). On that background, an over-dispersion of 6 over the 24 weeks in the main part of the current trial is deemed realistic.

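### After a thrombotic safety trigger, version 2 holds enrolment but sets no hold on dose escalation in current patients until the safety committee decides

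*Protocol*

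**What the plan says.** All references are to protocol version 2 (5 May 2017).

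- **Section 12.7** lists the triggers, among them a significant thromboembolic event, DIC and a death that may be related to trial product. Each holds enrolment and calls an urgent safety committee meeting. For patients already treated: "Dosing of patients on treatment may continue while further evaluation is made by the safety committee".
- **Section 5.3** says the same. When the criteria are met, "further enrolment in the trial will be halted", and dosing may go on during the evaluation.
- **Section 5.3.1** governs escalation. Three or more treated spontaneous bleeds within 12 weeks make a patient eligible. First, "the investigator must take into account the full clinical picture the patient is presenting with and all available laboratory results, including coagulation parameters". Then, for the second step: "If yes, and if investigator deems it safe, the patient will have to be dose escalated from 0.20 to 0.25 mg/kg". The first step, from 0.15 to 0.20 mg/kg, is worded in the same way. An unscheduled visit may be used if the next scheduled one is too late.
- **Section 8.1.9.4** applies this at each visit: "the investigator must evaluate if an escalation of the concizumab doses is needed according the escalation rules described in section" 5.3.1. Sections 8.1.9.5, 8.1.10.1 and 8.1.10.2 repeat it, so it covers visits 4 to 15.
- **Section 12.2** provides that "the investigator will be informed of any trial-related SAEs that may warrant a change in any trial procedure".
- **Section 6.4** stops trial product in the patient who has the thromboembolic event or DIC.

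Section 5.3.1, footnote p of the flow chart and the visit sections contain no reference to 12.7.

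**The concern.** Letting patients continue on their present dose during a safety review is a deliberate choice and is not questioned. Raising a dose is a different act, and the text does not separate the two. After a clinical thrombosis, a new patient may not start on the lowest dose, while a current patient at another site may still move to a higher one.

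The dose range rests on every level being predicted to stay below the exposure of the 0.80 mg/kg every-four-days cohort of explorer3, in which no clinical consequences were seen (3.1.2; 5.2, footnote 1). A thrombosis or DIC in this trial would put that premise under review. Section 5.2 also says that target-mediated disposition turns small dose differences into large concentration differences, and 12.6 says there is no antidote. The sponsor has itself treated raising the dose as the cautious decision point: in explorer3 its safety committee declined the next dose cohort because of coagulation changes and between-subject variation, without any clinical event (3.1.2).

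**Working it through.** The protocol gives no figure for this point, so there is none to reproduce. The first step compares the texts; the rest sizes the effect.

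**1. What acts between the trigger and the decision**

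| Provision | Effect in that interval | Holds escalation in an unaffected patient? |
|---|---|---|
| 12.7, 5.3 | Enrolment held, urgent meeting called, dosing may continue | No |
| 5.3.1 | Investigator weighs the patient's own picture and laboratory results, and must deem escalation safe | Only by individual judgement |
| 6.4 | Affected patient stops | No |
| 12.2 | Investigators told of SAEs that may warrant a procedure change | Gives no instruction on escalation |
| 12.8.2 | DMC recommends, safety committee decides | After review |
| 18.5 | Sponsor, ethics committee or regulator may stop all or part of the trial | Discretionary |
| 12.7, restart amendment | Needed to restart the trial | No; the same paragraph lets dosing continue |

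**2. When the enrolment hold has nothing left to hold**

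Inputs (section 7): recruitment 16 Aug to 16 Dec 2017 = 122 days = 17.43 weeks; 76 weeks of treatment. Assumptions: uniform entry, no dropout.

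Share of treatment time after enrolment closes = 1 − (17.43/2)/76 = **88.5%**. This counts treatment time, not escalations.

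**3. Upper bound on escalations from the planning figures**

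Section 17.1, for all main-part data: "it is expected that the treatment duration of the main part is on average 8 months with an average ABR of 5.4". For end-dose data it assumes an ABR of 4 over 6 months.

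- Bleeds per patient, all data: 5.4 × 8/12 = 3.6
- Bleeds per patient on the end dose: 4 × 6/12 = 2.0
- Bleeds outside the end dose: 3.6 − 2.0 = 1.6 per patient; × 33 = 52.8
- Each escalation uses at least 3 of these: 52.8/3 = 17.6, so at most **17** in the main part
- Per week: 17.6/(8 × 4.345) = 0.51, or about 1.0 per two weeks

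This is an upper bound because the 1.6 includes traumatic bleeds and run-in bleeds, which do not count towards escalation.

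**4. Simulation of the 5.3.1 rule**

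The rule as simulated: two-week run-in, at least 3 spontaneous bleeds in 12 weeks, escalation at the next scheduled visit, stop at 0.25 mg/kg on the same count.

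Assumed inputs:
- Spontaneous rate at 0.15 mg/kg: 2, 3, 4 or 5.4 per year. The last is 17.1's average for all treated bleeds, so it is a high case.
- Between-patient gamma shape = mean/(over-dispersion − 1). Over-dispersion 6 with 2.0 bleeds in 6 months gives 2.0/5 = 0.40. Over-dispersion 3 over 24 weeks gives 1.84/2 = 0.92 (0.9 used).
- Fall in rate per dose step: 0% or 50%.

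Results over the 16 combinations, 20,000 patients each:

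| Quantity | Range |
|---|---|
| Patients escalated, of 33 | 5.9 to 15.9 |
| Escalations in all | 7.0 to 26.0 |
| Share after enrolment closes | 87% to 96% |
| Escalations per week, closure to trial week 76 | 0.10 to 0.38 |
| Per 2-week review | 0.20 to 0.76 |
| Per 4-week review | 0.41 to 1.52 |

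That a minority escalates fits section 5.2: "The minority of patients which are predicted to have steady-state plasma concentrations below this threshold are expected to experience bleeding episodes". The protocol states no review length; the intervals are illustrations.

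**5. Size of one step**

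Section 5.2, footnote 1, gives maximum predicted exposure relative to 0.80 mg/kg every four days: at 0.20 mg/kg, more than 3 times lower (below 1/3); at 0.25 mg/kg, 35% lower (0.65). Ratio: 0.65/(1/3) = **at least 1.95-fold**, for a dose ratio of 0.25/0.20 = 1.25.

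**The case against.** The case against is substantial.

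- **Nothing is contradicted.** Titration is the regimen under test, and two sections state openly that dosing may continue. This stands: the point is an improvement in design, not an inconsistency.
- **Escalation is not automatic.** A reader might infer that the protocol forces sites to escalate during a review. It does not. The investigator must deem the step safe, that condition is not confined to the patient's own data, and an investigator told of a thrombosis under 12.2 may withhold it. What remains is that the outcome then depends on each site's knowledge and judgement.
- **The committee can act.** The closing sentence of 12.7 ties pausing or stopping dosing to similar SAEs and trends, and a reader might infer that the committee cannot pause dosing after a single thrombosis. The text does not support that. The urgent meeting decides further actions after any trigger, and 18.5 lets the sponsor stop part of the trial. The gap is only the time before the decision.
- **The interval should be short.** The SAE form is due within 24 hours and the meeting is urgent. This stands and keeps the expected number small.
- **Exposure stays within experience.** Even 0.25 mg/kg is predicted 35% below the explorer3 maximum, and single doses up to 9 mg/kg gave higher concentrations (3.1.2). That supports the dose range before an event; it does not settle whether to raise doses while an event is unexplained.
- **FVIII cuts both ways.** A held patient may bleed more and need more FVIII. The point therefore does not rest on FVIII co-exposure.
- **Trends are a poor trigger.** D-dimer and F1+2 rises are a known drug effect, so freezing escalation on laboratory trends is debatable. Accepted; the remedy leaves trends out.

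The DMC charter and the version 2 text after 18.5 are not available.

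**Conclusion.** The point holds in a narrow form. After a significant thromboembolic event, DIC or possibly related death, version 2 has no trial-level rule on escalation in other patients until the safety committee decides; only each investigator's judgement stands in the way. In this trial most treatment time falls after planned enrolment closes, when the one automatic restriction has nothing left to restrict.

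The size is modest: about 0.1 to 0.4 escalations per week of review. It rests on the assumed spontaneous rates, on enrolment to plan and on no dropout other than the rule's own stop at 0.25 mg/kg. It is conditional on a trigger, whose probability is not estimated. No excess risk of thrombosis can be derived from the protocol, so the 1.95-fold exposure ratio should not be read as a risk ratio, nor the 88.5% as a share of escalations. The change is worth making because it is cheap and protects patients; the case does not go further than that. Confidence is medium.

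**What to change.** Add to 5.3.1, with a cross-reference in 12.7:

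> When a significant thromboembolic event, DIC or possibly related death meets a 12.7 criterion, the sponsor promptly notifies sites and no patient is dose escalated until the safety committee has decided; patients on treatment stay on their current dose, and the decision states whether escalation may resume.

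Leave out the anaphylaxis, similar-SAE and trend triggers; the committee can decide those case by case.

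Cost: one sentence and a cross-reference, using the existing committee and the 12.2 notification route. The rule takes effect only once sites are told, so the notice must be prompt. The clinical downside is that an eligible patient waits for a higher dose until the urgent meeting decides, and section 17 expects a patient on a non-efficacious dose to bleed much like an untreated one. On the simulated rates this affects fewer than one patient per two-week review (0.20 to 0.76). FVIII is available for the bleeds, the held step can follow at an unscheduled visit, and 5.3.1 already recognises waits of up to 8 weeks for a scheduled visit in the extension part.
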